Zoster vaccine will be administered to healthy and HCV-infected individuals. Volunteers serum, PBMCs, and plasma will be collected at screening, days 0, 3, 7, 14, and 42 and batched for analysis to limit variations. In order to fully evaluate the immune signature generated by the zoster vaccine, we will determine the frequency and functionality of specific PBMC populations using flow cytometry and ELISpot assays. We aim to compare the data generated from this study to other published human system immunology and/or vaccination studies. To achieve this aim, our research group has adapted a flow cytometry panel designed to limit variations in standardizing human immunophenotyping. This flow cytometry panel is also currently being applied to the HBV vaccine study (CRI-0844). We will analyze intracellular cytokine staining and expression of cell surface markers on immune cells. IFN-gamma ELISpot assay has been used in older HZ vaccine studies to evaluate T-cell immune response post-vaccination. Commercially available VZV-derived peptides pools will be used to stimulate PBMCs in the ELISpot assay. VZV-specific antibody production post-immunization would also be assessed using commercially available VZV-ELISA kits.

AIM 2. Characterize the innate immune response to zoster vaccination by RNA-Seq analysis

RNA-seq will be used to evaluate innate immune activation by evaluating the changes to the expression levels of interferon-stimulated genes pre- and post-vaccination. In this pilot project, RNA will be isolated with using commercially available PAXgene tubes to immediately stabilize intracellular RNA profile and traditional homogenization of isolated volunteer PBMCs in Trizol prior to cryopreservation. RNA-seq sample preparation and sequencing will be performed at the Rockefeller University Genomics Resource center. The [name] research laboratory, with their extensive experience with RNA-seq will perform analysis of this data. Genome-wide mRNA expression profiles will be compared between the 2 arms of the study, healthy and chronically HCV infected volunteers. Gene expression levels will be quantified in relation to a reference standard of External RNA Control Consortium (ERCC) controls – a calibrated panel of defined RNA molecules at defined concentrations that will be “spiked in” to each library preparation to serve as a universal reference across samples.

12.5 * Primary Outcome(s)

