The primary analysis for the set of primary outcomes will search for statistical evidence of impairment in the innate and adaptive immune response in chronic-HCV subjects compared to age-matched Healthy Controls by testing the hypotheses that the variation from baseline to day 42 will differ between these two groups. To achieve this goal, we will apply two-sided paired t-tests and/or Wilcoxon tests for each one of the outcomes. Additionally, as a secondary analysis, we will fit a mixed-effects model that will use group (HCV – HC) and time (0,3,7,14, and 42 days) as fixed effects and a random intercept for each subject. This modeling strategy allows to infer about differences across time points, and also within time points, while controlling for multiple testing. Further evaluation of the immune signature generated by the zoster vaccine will be done with flow cytometry and ELISpot assays and qualitative comparisons with other

human system immunology and /or vaccination studies will be carried out. For the secondary outcomes, the analysis for the ISG expressions as measured by RNA-seq counts will be processed in *limma* package in R and the same formulation for mixed-effects model described previously will be applied to verify differences at gene-wise level. Serum biomarkers of immune activation will be compared across groups with paired t-tests and Wilcoxon test for each time point.

12.9 * Explain the rationale for the choice of statistical measures and the number of participants proposed for the study, including the power calculations when applicable.

A sample of n=40 (20 HCV / 20 HC) individuals provides 80% power at 1.6% (after Bonferroni correction for 3 outcomes) significance to detect minimum differences in biomarkers variation from baseline to day 42 as 1.08 standard deviations when applying two-sided paired t-tests. Since there is no preliminary data showing the degree of variability in the primary outcomes for the chronic HCV population, this pilot study will be valuable for future power analysis. To test for gene-wise differences between healthy and HCV-infected groups for a single time point, a sample size of n=20 individuals in each groups provides 80% power at 5% significance to detect effect sizes greater than 1.5 FCH (Fold-Changes), assuming a coefficient of variation as 40% and a depth of coverage greater than 20. Calculation was performed using the library RNASeqPower in R software version 3.2.1.

12.10 * Will samples be coded?

Yes No

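### Section 12.8 credits the mixed-effects model with multiplicity control that it does not provide, and names no procedure for the visit or gene-wise comparisons

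*Combined protocol and SAP*

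**What the plan says.** Section 12.8 plans, for the main analysis, t-tests and/or Wilcoxon tests of the change from baseline to day 42. It then adds: "Additionally, as a secondary analysis, we will fit a mixed-effects model". The model has group and "time (0,3,7,14, and 42 days) as fixed effects and a random intercept for each subject". No group-by-time term is listed. The next sentence gives the model's merit: "This modeling strategy allows to infer about differences across time points, and also within time points, while controlling for multiple testing". No gate, contrast adjustment, false-discovery rate or adjusted threshold follows.

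For RNA-seq, section 12.8 says that "the same formulation for mixed-effects model described previously will be applied to verify differences at gene-wise level", using limma. Aim 2 (section 12.4) sets the breadth: "Genome-wide mRNA expression profiles will be compared between the 2 arms of the study". Also in section 12.8, "Serum biomarkers of immune activation will be compared across groups with paired t-tests and Wilcoxon test for each time point", again with no adjustment stated.

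The only stated multiplicity adjustment is in the section 12.9 power statement: "80% power at 1.6% (after Bonferroni correction for 3 outcomes) significance", for "minimum differences in biomarkers variation from baseline to day 42 as 1.08 standard deviations when applying two-sided paired t-tests". The gene-wise power in the same section uses 5% significance at a single time point, without reference to the number of genes.

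**The concern.** A random intercept handles the correlation between measurements on one subject. Fitting all visits together also gives a shared variance estimate. Neither limits the chance of a false positive over several contrasts from the model, or over thousands of separate gene-wise fits. The text therefore states a property that the method lacks, and it does so where a reader would look for the multiplicity rule.

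This matters because the sentence tells the analyst that the issue is settled. Section 12.7 records that analysis of the stored samples passed to a different investigator in 2019, so the written text carries weight. Aim 2 rests on the gene-wise analysis, and section 12.1 hopes to identify targets for vaccine optimization. Nominal 5% results presented as controlled would put chance findings into that list.

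**Working it through.** **Inputs.** From sections 12.8 and 12.9: 20 per group; five visits; 1.6% two-sided for the day-42 comparison; gene-wise 5%, 80% power, 1.5-fold change, coefficient of variation 40%, depth 20. Assumed, because the documents do not give them: between-visit correlation, number of genes, and proportion of genes that truly differ.

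**1. The plan's gene-wise figure.** n = 2(z₀.₉₇₅ + z₀.₈₀)²(1/depth + CV²)/(ln FC)² = 2 × (1.960 + 0.842)² × (0.05 + 0.16)/(0.4055)² = 20.05 per group. Power at n = 20 is 79.9%. The figure reproduces with an unadjusted two-sided 5% per gene.

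**2. What the Bonferroni level covers.** 0.05/3 = 1.67%, written as 1.6%, spent on three outcomes for one comparison over time. At 1.6% with 20 per group, an independent two-sample t-test has 80.9% power for 1.08 SD. (A paired test on 20 pairs would have 97.9%; that mismatch is a separate point.) Nothing here reaches visits or genes.

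**3. Does the model itself control multiplicity?** Data were simulated with no group difference (20 per group, five visits, random intercept, 20,000 trials per correlation), and group contrasts were tested at 5% each.

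| Within-subject correlation | Single contrast | Any of 5 visits | Any of 4 changes from baseline |
|---|---|---|---|
| 0.2 | 4.9% | 21.6% | 14.9% |
| 0.5 | 4.9% | 17.8% | 15.5% |
| 0.8 | 5.0% | 12.4% | 15.6% |

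Each contrast keeps its level; the family does not. Adding Bonferroni brings the family to 2.9-4.7% (five visits) or 4.0-4.4% (four changes). The control comes from the adjustment, not from the model.

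**4. Familywise error by correlation.** 400,000 draws of equicorrelated normals, counting any |z| > 1.96:

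| Correlation | 5 visits | 4 post-vaccination visits |
|---|---|---|
| 0 | 22.6% (1 − 0.95⁵) | 18.5% (1 − 0.95⁴) |
| 0.5 | 18.2% | 15.6% |
| 0.7 | 14.8% | 13.2% |

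**5. Gene-wise false positives.** Expected number per contrast if all nulls are true = 0.05 × number of genes: 15 for 300, 500 for 10,000, 1,000 for 20,000.

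**6. Gene-wise power under a 5% false-discovery rate.** For a per-gene threshold a, power(a) = Φ(2.798 − z₁₋ₐ/₂), where 2.798 = 0.4055 × √(20/(2 × 0.21)). With a proportion π of genes truly different by 1.5-fold, solve (1 − π)a / [(1 − π)a + π·power(a)] = 0.05:

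- π = 1%: a ≈ 0.00006, power 11%
- π = 5%: a ≈ 0.0008, power 29%
- π = 10%: a ≈ 0.0024, power 40%

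A cruder approximation sets the threshold as if power were already 80%, a = 0.05 × 0.8π/[0.95(1 − π)]. It gives 23%, 40% and 49%, which is too favourable at n = 20. Its sample sizes for a true 80% are consistent: about 49, 39 and 35 per group.

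**7. Cost per visit.** Noncentral t, 20 per group, 80% power: detectable difference 0.91 SD at 5%, and 1.10 SD at Holm's first step (0.05/4 = 1.25%).

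**The case against.** **The written model has no family of visit-specific group tests.** With group and time additive, the group difference is one parameter, the same at every visit. Its test has about 5% error per outcome (4.9% in simulation at correlation 0.5). A reader might infer that the model as written already runs at 18%. The documents do not support that: the figures in steps 3 and 4 apply only if visit-specific contrasts are taken. The plan does promise inference within time points, so such contrasts appear intended, and comparisons across time points form a family even in the additive model. The false attribution stands either way, but its size for group contrasts is conditional.

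**Control is intended, only its method is missing.** A reader might infer that the comparisons will certainly be reported unadjusted. The text does not say so. It claims control and omits the procedure, and an analyst could still use adjusted contrasts or adjusted gene-wise p-values. The 5% in the gene-wise power statement suggests unadjusted testing, but it is a power input and not a decision rule. For genes, only the model formulation is carried over; no explicit claim of control is repeated there.

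**Scope.** The model is secondary and section 12.9 calls the study a pilot. That would justify labelling the results exploratory and leaving p-values unadjusted. It does not justify describing them as controlled.

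**Conclusion.** The point holds as a false stated property with no procedure behind it, confined to the secondary and gene-wise analyses. The baseline-to-day-42 comparison has its own stated level and is not touched.

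If visit-specific group contrasts are tested at 5% each, familywise error per outcome is about 18% over five visits (15-23% for correlation 0.7 to 0) or 16% over four post-vaccination visits (13-18.5%). Gene-wise, 15 to 1,000 false positives per contrast are expected for an assumed 300 to 20,000 genes with all nulls true.

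A reader might go further and compound the error over outcomes, or multiply a single gene count by four visits. The documents do not support a firm figure of either kind: they give no correlation between outcomes and no number of genes, and the written model has no visit-specific group effects.

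The section 12.9 gene-wise power of 80% is arithmetically right, but only per gene at an unadjusted 5%. It cannot stand beside a false-discovery rate.

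**What to change.** In section 12.8:

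- Delete the claim that the model controls for multiple testing.
- Add the group-by-time term. For each outcome, use its overall test at 5% as a gate, then report Holm or multivariate-t adjusted p-values for the four post-vaccination contrasts. State whether these are group differences at the visit or differences in change from baseline.
- Label these results as secondary and controlled within each outcome only. Nothing here controls error across outcomes.
- In limma, apply a 5% Benjamini-Hochberg false-discovery rate across genes and contrasts.

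In section 12.9, restate the gene-wise power as 80% per gene at an unadjusted 5%, and add the power under the false-discovery rate with its assumptions: roughly 11-40% for a 1.5-fold change at 20 per group if 1-10% of genes truly differ.

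Cost: SAP text and standard software options, with no change to enrolment, visits or assays. There are two real losses. The detectable per-visit difference at Holm's first step moves from 0.91 to 1.10 SD, and the stated gene-wise power becomes much less favourable.

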Indicate which **variable(s)** will be assessed to judge the primary specific aim. Give measurement units, if applicable.

We will measure the following parameter:

- **Serum zoster antibody levels by gpELISA expressed in (units/ml)**

12.6 * Secondary Outcome(s)

Indicate which **additional variable(s)** will be assessed to judge the secondary outcome(s). Give measurement units, if applicable.

- **Interferon-stimulated gene (ISG) expression in PBMCs expressed as fold-change (FCH) above baseline**
- **Serum biomarkers of innate immune activation (expressed in %)**
- **Responder cell frequency: VZV specific CD4+ T cells post-vaccination (expressed in %)**
- **Interferon-gamma response by ELISpot expressed as number of spot-forming cells per 10^6 PBMCs**

12.7 * Methods and Procedures

Please provide a description of the laboratory and clinical analyses and procedures that will be performed. Include the role of external collaborators and consultants when appropriate. Please refer to Help text for Guidance.

This study is an open-label protocol divided into the healthy versus chronic HCV volunteer arms. The study will be advertised in local newspapers and different online resources. Potential participants identified with the aid of the Bellevue Hospital Center Hepatitis clinic and other local physicians, will be asked to call [name] ([name]), if they are interested in the study.

Our aim is to screen and enroll 20 age-matched (\pm 5 years) and gender-matched individuals between 50 and 60 years of age into each arm of the study. Individuals recruited into the study must be HIV and hepatitis B negative, without a history of vaccination within the past month, no history of immunosuppressive therapy, active malignancies or herpes zoster reactivation. Baseline screening tests (HIV ELISA, hepatitis B anti-surface and core antibodies, hepatitis C antibody, viral load and genotyping, complete blood counts and a comprehensive metabolic panel) will be obtained prior to enrolling in the study. HCV viral load and genotyping: will be determined by clinical laboratory analysis. Patient blood samples will be sent to a CLIA certified reference laboratory for analysis.

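### The between-arm test of serum biomarkers at each visit has no stated baseline reference, so it mixes a pre-existing HCV difference with the vaccine response; the ISG model should name its group-by-time term

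*Combined protocol and SAP*

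**What the plan says.** - **Serum biomarkers, analysis (12.8):** "Serum biomarkers of immune activation will be compared across groups with paired t-tests and Wilcoxon test for each time point". This is the only sentence that names a test for this outcome.
- **Serum biomarkers, definition (12.6):** the entry "Serum biomarkers of innate immune activation (expressed in" ends in a percent sign and does not say percent of what.
- **Primary analysis (12.8), for contrast:** "testing the hypotheses that the variation from baseline to day 42 will differ between these two groups". Here the baseline reference is explicit.
- **ISG expression:** Aim 2 in 12.4 speaks of "evaluating the changes to the expression levels of interferon-stimulated genes pre- and post-vaccination", and 12.6 defines the outcome as a fold-change over baseline. The analysis in 12.8 takes RNA-seq counts, and "the same formulation for mixed-effects model described previously will be applied to verify differences at gene-wise level". That model enters group and time (day 0 included) "as fixed effects and a random intercept for each subject". No group-by-time term is named. The RNA-seq sizing in 12.9 begins "To test for gene-wise differences between healthy and HCV-infected groups for a single time point".
- **Arms and expected baseline (12.7):** the arms are healthy and chronic-HCV volunteers, matched on age and gender only. The section describes persistent innate activation in chronic HCV and refers to high ISG expression before therapy.
- **Samples (12.4):** serum, PBMCs and plasma "will be collected at screening, days 0, 3, 7, 14, and 42 and batched for analysis".

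**The concern.** The hypothesis in 12.3 is an impaired response after vaccination. A comparison of levels at a post-vaccination visit estimates the baseline difference between arms plus the difference in response, and cannot separate the two. Randomisation would make the first part zero on average. Here the protocol itself gives a reason to expect it not to be zero. Matching on age and gender does not balance the biomarker.

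The error can go either way. If both arms respond identically, a raised HCV baseline produces significant differences that look like a vaccine effect. If the HCV arm responds less, the raised baseline offsets the deficit and the test may find nothing. Serum biomarkers and ISG expression are the only innate outcomes listed in 12.6, so the innate part of the hypothesis depends on how these two are analysed.

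**Working it through.** **Inputs.** From the documents: 20 per arm; visits at days 0, 3, 7, 14 and 42; for RNA-seq, 5% level, 80% power, 1.5-fold, CV 40%, depth 20. Assumed, because the documents give none: two-sided 5% for the serum tests, baseline gap *d* in SD units, within-subject correlation *r* (equal between all visits), within-pair correlation *c*, and a 0.9 SD impairment.

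**1. The plan's nearest figure (12.9, RNA-seq at one time point).** n = 2(z₀.₉₇₅ + z₀.₈₀)²(1/depth + CV²)/ln(FC)² = 2 × 7.849 × (0.05 + 0.16)/0.1644 = 20.05 per group. It reproduces, as a comparison of levels. On the same inputs, a pre-existing 1.25-, 1.5- or 2-fold difference would be flagged at one visit in 34%, 80% or 99.8% of trials with no difference in response.

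**2. Serum level test, identical response in both arms.** Unpaired t: noncentrality d√(n/2) = 3.162d, 38 df, critical value 2.024. Rank-sum rates come from 4,000 simulated trials.

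| Baseline gap (SD) | Noncentrality | Unpaired t | Rank-sum |
|---|---|---|---|
| 0.25 | 0.79 | 12% | 12% |
| 0.5 | 1.58 | 34% | 33% |
| 0.8 | 2.53 | 69% | 67% |
| 1.0 | 3.16 | 87% | 85% |

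Paired t, as the plan words it: noncentrality d√n/√(2(1−c)), 19 df, critical value 2.093. At d = 0.5 and c = 0, 0.2, 0.4 this is 1.58, 1.77, 2.04, giving 32%, 39%, 49%. Pairing does not remove the gap.

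**3. The same situation, baseline-referenced.** In 20,000 simulated trials per setting (gap 0, 0.5, 1.0 SD; r = 0.5, 0.8), change from day 0 was significant in 4.6% to 5.3% and the group-by-time test in 4.7% to 5.1%.

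**4. Masking.** The HCV response is 0.9 SD lower and the HCV baseline is raised by g. The level test sees a net difference of 0.9 − g, with noncentrality 3.162(0.9 − g). Rates are for detection in the impaired direction.

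| Gap g (SD) | Net difference | Noncentrality | Detected |
|---|---|---|---|
| 0 | 0.90 | 2.85 | 79% |
| 0.25 | 0.65 | 2.06 | 52% |
| 0.5 | 0.40 | 1.26 | 23% |
| 0.8 | 0.10 | 0.32 | 5% |

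For change from day 0, the SD is √(2(1−r)) = 1.183, 1.000, 0.775 at r = 0.3, 0.5, 0.7. Noncentrality is 0.9 × 3.162/SD = 2.41, 2.85, 3.67, and detection is 65%, 79%, 95% whatever the gap.

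**5. ISG, only if the model is strictly additive and its group term is the deciding test.** The group term then compares subject means over five visits, with SD √((1+4r)/5) = 0.663, 0.775, 0.872 at r = 0.3, 0.5, 0.7. With a 0.5 SD gap and identical response it is significant in 64%, 51%, 42% of trials. This is one gene at an unadjusted 5%. At r = 0.5 the 51% falls to 27% at a 1% threshold and 8% at 0.1%. A random intercept does not absorb a systematic difference between arms; that difference goes into the group term.

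**The case against.** **No baseline-referenced innate test exists.** A reader might infer this, but the documents do not settle it. Section 12.8 opens by looking for impairment of the innate as well as the adaptive response through change to day 42 and applies its tests to every outcome. Section 12.9 corrects for three outcomes. An innate day-42 change test may therefore be intended. Against that, 12.5 lists antibody alone as primary, and nothing carries the change test to days 3, 7 and 14.

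**The ISG model has the same fault.** This is also tempting and too strong. Section 12.8 says the model supports inference both across and within visits. A strictly additive model gives one constant group difference and could not do the latter, so a group-by-time term was probably meant. The fold-change definition in 12.6 points the same way. What stands is that the term is not stated, nothing names the deciding contrast, and a fold-change outcome (constant at day 0) does not fit a model of counts that includes day 0.

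**The percent unit may mean percent of baseline.** If so, the serum test would already be baseline-referenced. The documents do not say so.

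**Day 0 is presumably one of the time points.** A day-0 test would show a gap but would not remove it from later tests.

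**Comparing levels is itself an aim.** Sections 12.4 and 12.7 do compare expression profiles between arms. That is legitimate as description, but it does not test the hypothesis in 12.3.

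**The gap sizes are assumed.** This stands. Section 12.7 gives a direction only, and its ISG sentence concerns response to interferon therapy within chronic HCV, not a measured gap against healthy controls.

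**Conclusion.** The point holds for serum biomarkers. As written, the per-visit test cannot distinguish an existing HCV difference from a difference in vaccine response. Across assumed gaps of 0.25 to 1.0 SD it is significant in 12% to 87% of trials with identical responses, and a 0.5 SD gap cuts detection of a 0.9 SD impairment from 79% to 23%. These rates rest on normal data, equal variances, an additive response and assumed gaps and correlations.

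For ISG the point is narrower: the group-by-time term should be named, and the rates in step 5 apply only if it was not intended. The primary change-to-day-42 test is not affected. For responder cell frequency and ELISpot, 12.8 names no specific between-arm test, so nothing is claimed about them. The fault lies in the stated test, not in the data, and should be corrected before analysis.

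**What to change.** - **Serum biomarkers.** State what the percent refers to. Replace the per-visit level test with a between-arm test of change from day 0 at days 3, 7, 14 and 42, or the equivalent group-by-time contrasts against day 0 from the mixed model. Fix the scale in advance: log-ratio to day 0 for concentrations or skewed markers, simple change only where an additive response is expected. Report the day-0 comparison separately, as a description of baseline.
- **ISG.** Name the group-by-time term in the limma/mixed model, make its contrasts against day 0 the test of vaccine response, and reconcile the fold-change definition with the model of counts.
- **Scope.** Say whether the day-42 change test covers any innate outcome.

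**Cost.** SAP wording and a little more analysis; no new samples. With no baseline gap and r below 0.5, change has less power than level: 65% against 79% at r = 0.3 for 0.9 SD (equal at r = 0.5; 95% against 79% at r = 0.7). Scale matters: for an assumed lognormal marker (log SD 0.3 to 0.8, r 0.5 to 0.7) with an identical two-fold rise and a 0.5 SD gap, raw change is significant in 10% to 17% of simulated trials, against 5% for the log-ratio. Baseline covariate adjustment is another option but not equivalent in unrandomised arms: with equal mean change it leaves d(1−r), for example 0.5 × (1 − 0.5) = 0.25 SD.

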The team will identify multiple members of the patient community, as well as outreach and harm-reduction workers with experience referring HCV infected volunteers to clinical research, in order to engage patients in the design of the study, including aspects of recruitment, conduct, retention, and the analysis and sharing of results. Patients and other will be invited to face-to-face meetings with the research team and support staff (or teleconference if preferred), and will be compensated for their time /effort. Patient stakeholders engaged in this way are not expected to enroll into the study; any exploration of their enrollment would be made separately, free of undue influence

12.3 * Hypothesis

Describe the ***research hypothesis*** in a single sentence.

We hypothesize that individuals with chronic HCV infection will demonstrate impaired innate and adaptive immune responses following zoster vaccination.

12.4 * Aim(s)

Indicate how you will **address the hypothesis** (e.g., to compare groups, to estimate a parameter, to ascertain feasibility). Since the sample size determination is usually based on the primary aim only, the primary aim should be sufficient to justify the study.

AIM 1: Characterize the adaptive immune response to zoster vaccination in chronic HCV infection

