Flow cytometry, ELISpot and ELISA analyses will be performed on PBMCs to determine B-cell and T-cell proliferation and polyfunctionality. we will determine the frequency and function of specific PBMC populations using flow cytometry and ELISpot assays. For flow cytometry, we will utilize an antibody panel designed to limit variations in standardizing human immunophenotyping to assess intracellular cytokine staining and expression of cell surface markers on immune cells. IFN-gamma ELISpot assay has been used in older HZ vaccine studies to evaluate T-cell immune response post-vaccination. We will utilize commercially available VZV-derived peptide pools will be used to stimulate PBMCs in the ELISpot assay. VZV-specific antibody production post-immunization would also be assess using commercially available VZV-ELISA kits. A multiplex Luminex assay targeting TNF-alpha, IFN-gamma, IL-2, IL-4, IL-17 and other cytokines will be performed on plasma samples. Flow cytometry and multiplex cytokine assays will be performed with the assistance of the Translational Technology Core Laboratory Resource center.

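### Section 12.8 tests serum biomarkers between arms at every visit with two tests, no key visit, no error control and no exploratory label, and does not account for expected baseline differences

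*Combined protocol and SAP*

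**What the plan says.** Section 12.6 lists, as a secondary outcome, "Serum biomarkers of innate immune activation (expressed in" per cent, without naming or counting the markers. The only analysis sentence for them is in section 12.8: "Serum biomarkers of immune activation will be compared across groups with paired t-tests and Wilcoxon test for each time point". The visits, taken from the mixed-model sentence in the same section, are "time (0,3,7,14, and 42 days) as fixed effects".

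Three other statements bear on error control, and none clearly reaches these tests.

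- The primary analysis in 12.8 concerns the change from baseline to day 42, for the set of primary outcomes.
- The remark in 12.8 about controlling for multiple testing describes the mixed-effects model. Section 12.8 extends that model to interferon-stimulated gene expression, then gives the serum biomarkers their own stand-alone tests.
- Section 12.9 uses "1.6% (after Bonferroni correction for 3 outcomes) significance" for the change from baseline to day 42. It does not say which three outcomes are meant, and 12.5 lists one primary outcome.

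The hypothesis in 12.3 is that "individuals with chronic HCV infection will demonstrate impaired innate and adaptive immune responses following zoster vaccination". Section 12.7 states separately that chronic HCV goes with persistent innate immune activation.

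**The concern.** Read literally, each biomarker gives five between-arm comparisons, each made by two tests. Nothing written beforehand says which visit or test decides, so a nominally significant result at any visit could become the reported finding. The biomarkers and the gene-expression outcome are the two explicitly innate measures in 12.6, so such a finding could be presented as evidence on the innate half of the hypothesis.

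There is a second problem, which multiplicity adjustment alone does not cure. The hypothesis is about the response after vaccination, but the stated comparison is of levels at each visit. If the arms already differ on day 0, as 12.7 leads one to expect, they can differ on days 3 to 42 with no difference in response. A significant result would then be a real difference in level but the wrong answer to the question.

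**Working it through.** **The plan's own figure.** The plan gives no error rate or power for these tests. The nearest figure is in 12.9: "80% power at 1.6% (after Bonferroni correction for 3 outcomes) significance" with "A sample of n=40 (20 HCV / 20 HC) individuals" for a difference of 1.08 SD. As a two-sample t-test, the noncentrality is 1.08 × √(20/2) = 3.42 on 38 degrees of freedom. Power at two-sided 1.6% is 80.9%, and the difference detectable with 80% power is 1.07 SD. The figure reproduces on that basis. A paired test on 20 pairs, with 1.08 in SDs of the pair differences, would give 97.9%. The figure says nothing about visit-by-visit biomarker tests.

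**Inputs for the error rate.**
- 20 per arm (12.9).
- Five visits (12.8), or four if day 0 is left out.
- 5% two-sided per test: an assumption, as 12.8 states no level.
- Number of biomarkers: an assumption. Section 12.7 says "A multiplex Luminex assay targeting TNF-alpha, IFN-gamma, IL-2, IL-4, IL-17 and other cytokines will be performed on plasma samples". That names five, but in plasma, while the outcome is in serum, so five is an illustration.
- Correlations between visits and between biomarkers: assumptions.

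**Independent tests, one test type.** The chance of at least one false positive in k tests is 1 − 0.95^k.
- One biomarker, five visits: 1 − 0.95^5 = 22.6%. Four visits: 1 − 0.95^4 = 18.5%.
- Five biomarkers, five visits: 1 − 0.95^25 = 72.3%. Four visits: 1 − 0.95^20 = 64.2%.

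**Correlated tests, by simulation.** No arm difference at any visit, normal data, five visits, a positive from either test counted. The middle columns use 4,000 replicates of 20 v 20 with correlation 0.5 between biomarkers. The last column uses 10,000 runs of 20 pairs, from strong correlation (0.8 between visits, 0.6 between biomarkers) to independence.

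| Biomarkers | Visit correlation 0.5 | Visit correlation 0.8 | Strong correlation to independence |
|---|---|---|---|
| 1 | 22.4% | 15.7% | 15-26% |
| 2 | 35.6% | 25.9% | not run |
| 3 | not run | not run | 33-59% |
| 5 | 61.2% | 47.1% | 44-78% |
| 10 | not run | not run | 61-95% |

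A further run gave 15-21%, 26-37% and 49-63% for one, two and five biomarkers. Paired and unpaired versions agree closely (one biomarker 22.2% and 15.9% paired; five 61.0% and 46.8%). With four post-vaccination visits, one biomarker gives 19.0% or 13.7%.

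**Share due to running both tests.** For a single comparison, counting either test raises the error from about 5.0% to 5.9%. For one biomarker over five visits, it rises from 19.2% to 22.4% at visit correlation 0.5, and from 13.2% to 15.7% at 0.8. The two tests use the same data and mostly agree.

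**Baseline difference.** Suppose the arms differ by a constant 0.5 SD at every visit, day 0 included, and the vaccine response is the same in both (0.5 is an assumption).
- Raw test at one visit: noncentrality 0.5 × √10 = 1.58 on 38 degrees of freedom, so it rejects in about 34% of trials.
- Raw test of the mean of four post-vaccination visits: the mean has variance (1 + 3ρ)/4. At ρ = 0.5 that is 0.625, so the standardised difference is 0.5/√0.625 = 0.63 and it rejects in about 50%. At ρ = 0.8 the variance is 0.85, the standardised difference 0.54, and it rejects in about 39%.
- Change from baseline: the constant cancels and rejection stays near 5%.

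**The case against.** The strongest reply is about weight. This is one secondary outcome in a study that calls itself a pilot, the primary conclusion does not rest on it, and unadjusted secondary comparisons at this size are common. That stands and keeps the priority low. It does not supply the missing label: the pilot wording in 12.9 concerns future power analysis, and the same paragraph powers formal tests.

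A second reply is that the 1.6% level might be meant for these tests too, because 12.9 speaks of variation in biomarkers and leaves its three outcomes unnamed. The plan does not settle this. Even if 1.6% were borrowed, independent tests of one type over five visits would give 1 − 0.984^5 = 7.7% for one biomarker and 1 − 0.984^25 = 33% for five.

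Three stronger readings are tempting, and the documents do not support them.
- That a false innate finding is likely. This depends on the panel size, which is not given. With one or two biomarkers the rate is well below one half, and with five it lies on either side of one half, depending on the correlations.
- That using two tests is the main fault. It adds little.
- That the innate conclusion would turn on a single biomarker p-value. Aim 2 and 12.7 assign the innate response to RNA-seq, and 12.8 ties evidence of impairment to the change from baseline to day 42.

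**Conclusion.** The point holds as a minor one. As written, the serum-biomarker analysis has an uncontrolled and inflated false-positive rate: about 15-22% for one biomarker and about 47-63% for five, against 5% for a single test. These figures assume 5% per test, five visits, visit correlation of roughly 0.5 to 0.8 and no true arm difference; the wider correlation range gives 15-26% and 44-78%. The inflation is present for any panel size, but how large it is cannot be fixed from the documents.

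The assumption of no arm difference is itself doubtful given 12.7. For that reason the choice of raw level over change from baseline matters at least as much as the number of tests.

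**What to change.** Replace the serum-biomarker sentence in 12.8 with wording that does the following.

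1. List the biomarkers.
2. Give each one prespecified test of the between-arm difference in change from baseline. Use either day 0 to day 42, as in the primary analysis, or a joint group-by-time test from the mixed model already in 12.8. The second option needs the interaction term written out, since 12.8 names only group and time.
3. Apply Holm or Benjamini-Hochberg across the listed biomarkers, or state that the whole family is exploratory.
4. Report visit-by-visit comparisons as exploratory estimates with confidence intervals, and keep the Wilcoxon test as a sensitivity analysis that cannot support a claim alone.

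The cost is wording only, with no new samples or assays. An effect confined to one visit becomes harder to establish. With five biomarkers, the strictest adjusted level is 0.05/5 = 0.01, and the two-sample difference detectable with 80% power rises from 0.91 to 1.13 SD of the change. Adjusting over all 25 visit-level tests instead (0.05/25 = 0.002) would need 1.33 SD. Using change need not lose precision: its SD is √(2(1 − ρ)) times that of a single visit, which is 1.00 at ρ = 0.5 and 0.63 at ρ = 0.8.
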